### 7.7 Trial assessments

Assessments will be conducted at each school at baseline (estimated January – July 2024) and at post-intervention (estimated November 2025 – May 2026). The post-intervention assessment will be completed approximately 18 months after the OPAL programme begins. Given that the programme takes 18 months to complete, this is an immediate post-intervention assessment point.

The same measures will be completed at each assessment, as detailed above, with the exception of the qualitative and process evaluation interviews (as detailed above) and the Tools for Schools resource use measure, which will only be completed by parents at post-intervention.

## 7.8 Long term follow-up assessments

There is no long term follow-up planned due to funding restrictions.

#### 7.9 Qualitative assessments

One to one qualitative interviews will be conducted with children and school staff, as detailed in the table above. Interviews will be transcribed and analysed using inductive thematic analysis. A process evaluation will also be included, which will include interviews will key school staff regarding the intervention and the research (see table above).

#### 7.10 Withdrawal criteria

Given the focus of the intervention, we do not anticipate that it would be necessary to withdraw a school from the trial (nor an individual child) for medical reasons.

Given that this is a feasibility trial, any situation where a school withdrew would be documented and, where possible, a process evaluation interview would be conducted to gain a better understanding of the decision to withdraw.

## 7.11 Storage and analysis of clinical samples

n/a

#### 7.12 End of trial

n/a

#### 8 Intervention

The OPAL programme will provide participating schools with an experienced mentor who supports the school over the course of an 18-month period to change their playtimes. The schools have autonomy over decision-making and they implement all aspects of the programme themselves in ways that work for them. The mentors are there to provide advice and guidance, not to deliver any of the implementation. The programme includes six planned sessions with the school which each has a specific focus. The first, for example, focuses on auditing the current play provision at the school and setting goals for the programme, later sessions include a training session for staff where they learn about theory and practice in playwork. Playworkers are trained to create environments to ensure play opportunities are as diverse and inclusive as possible, to observe, reflect and analyse the play that is happening and to make changes to the environment if needed. The guiding principle underlying this approach is that where possible play should be freely chosen, child led and intrinsically motivated. Often adults make choices about what children should play and set constraints and rules around children's play (e.g. 'lets play hide and seek, you hide I'll count'). Playwork training helps adults working with children to understand that their role is to create a playful environment and then to step back and allow children to lead the play. When children direct their own play, in a diverse environment they will naturally challenge themselves in their play in a way that is stretching but appropriate for them. The play programmes therefore increase adventurous play by working to provide children with more space and permission to lead their own play. In addition, schools would be encouraged to

introduce loose parts for play such as tyres and milk crates which give children more opportunity for creative, child-led play which may be adventurous in nature. Further sessions provided as part of the programme include what is called risk-reframing training for teachers and parents. During these sessions teachers and parents are taught how to implement the risk benefit approach recommended by the Health and Safety Executive (see https://www.hse.gov.uk/entertainment/childs-playstatement.htm). This approach requires adults to consider risks in the contexts of benefits rather than taking a risk minimisation approach; often a risk also provides a learning opportunity (benefit) and therefore the risk may be justified because of the benefits it offers. For example, a balance beam has a risk that a child will fall off and hurt themselves, but it has the benefit of giving children an opportunity to practice balancing and to develop their balance skills. The final sessions focus on including play within school policies and documentation and ending the mentoring with future planning and goal-setting. Initial evidence shows that when programmes of this nature are implemented, children become more physically active, take more risks in their play, and become more social and creative [13]. We have just completed a pilot study working with two schools who implemented the OPAL intervention. In the pilot study we conducted baseline and post-test data with two schools, who both successfully completed the OPAL programme and reported positive outcomes; the process of working with these pilot schools has informed the design of this study. As a result of the pilot work we have tested most of the procedures that we will use in this study and made some adaptations based on our learning and the feedback from the schools (e.g. increasing the window for the intervention to 18 months).

### 10 STATISTICS AND DATA ANALYSIS

The primary objective is to examine feasibility. The analysis will therefore focus on the following:

- Whether any serious concerns or serious negative impacts have arisen about the acceptability of study procedures or impacts of the intervention. This will be based on informal communication with the schools, formal communication with the schools, as well as the process interviews and qualitative interviews.
- The number of schools who were successfully recruited, randomised and retained throughout the study (including a record of those who were approached but declined or withdrew).
- Participation rates at intervention and control schools for the following measures:
  - 1. teacher-reported SDQ at baseline and post-intervention.
  - 2. child-report Stirling Wellbeing Questionnaire at baseline and follow-up for children in year 3 and 4 at baseline.
  - 3. Comparison using chi-square analysis of those with missing data vs. complete data on teacher report SDQ on demographic characteristics.
- Baseline to post-intervention comparisons of the following measures of children's play:

- 1. scan observations
- 2. focal observations
- 3. child-report
- 4. school-staff report,
- reliability analysis for:
  - 1. scan observations
  - 2. focal observations
  - 3. observation of physical activity.
- Proportion of missing data on measures used capture range of costs and benefits.

In addition, inductive thematic analysis will be used to analyse the qualitative interviews, with a focus on whether the costs and benefits described are captured in the battery of questionnaires and observation.

Inductive thematic analysis will be used to conduct the process evaluation, once transcribing and coding are complete.

As this is a feasibility study, significance tests will not be performed. Intervention effects will be represented by point estimates and their standard deviations. Point estimates will be calculated by subtracting unadjusted mean data at post-intervention from the mean data at baseline. These will be used along with their standard deviations to inform sample size calculations for a definitive trial, if appropriate.

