#### Green criteria:

- No serious concerns have arisen about the acceptability of study procedures
- At least 7/8 schools are successfully recruited, randomised and retained throughout the study
- Participation rates at intervention and control schools retained in the trial are at least:
  - 80% of teacher-reported SDQ at baseline. 80% retained at follow-up.
  - 80% of child-report Stirling Wellbeing Questionnaire at baseline. 80% retained at follow-up.
- No marked differences in the characteristics of the children with missing data on teacher report measures when compared to those with complete data.
- Evidence that play has improved at intervention schools, based on at least two of the following: scan observations, focal observations, child-report and school-staff report,
- There is evidence of at least good reliability for scan observations, focal observations and assessment of physical activity.
- Measures used capture range of costs and benefits based on process evaluation and qualitative interviews.

- No serious negative impacts have arisen.

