### Amber criteria (where no amber criteria exist, the green criteria apply):

- At least 6/8 schools are successfully recruited, randomised and retained throughout the study
- Participation rates at intervention and control schools retained in the trial are at least:
  - 60% of teacher-reported SDQ at baseline. 80% retained at follow-up.
  - 60% of child-report Stirling Wellbeing Questionnaire at baseline. 60% retained at follow-up.
- Any differences in the characteristics of the children with missing data on teacher report measures (when compared to those with complete data) are able to be handled successfully via statistical methods.
- There is evidence of at least adequate reliability for scan observations, focal observations and assessment of physical activity.

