#### 5 TRIAL SETTING

The trial will be run through eight participating schools. Participating schools will be referred to the trial through OPAL once they have approached them and agreed to do the programme.

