#### 6 PARTICIPANT ELIGIBILITY CRITERIA

#### 6.1 Inclusion criteria

Schools must be at least single form entry (~30 children per year or more). Schools will initially be recruited through pre-specified regions covering the SW of England (Cornwall, Devon, Bristol, Bath, Dorset and Wiltshire). If necessary this area may be expanded.

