### 7.2 Consent

Headteachers will be given detailed study information sheets and will provide informed consent for the school to participate in the research. The OPAL intervention falls within usual curriculum and other institutional activities (BPS, code of human ethics 2010, p.17) so no additional consent from parents is required for the intervention to be ran at the school. The headteacher will provide informed consent for all children in their care in Years 3 and 4 at baseline to complete questionnaires and for teachers of children in Year R to Year 4 to complete a questionnaire for all children in their class. They will also give consent for playtimes to be observed, but only in a way that does not lead to individual-level data (e.g. how many children are climbing?).

Parents will have a right to refuse their child's participation and children will have the right to refuse to participate. In both cases, no reason needs to be given and there will be no adverse consequences.

Children will be told about the research generally in a school assembly led by the research team, once before the baseline data collection, and again before the post-test data collection. During this assembly we will give children the opportunity to ask questions and explain what they should do if they don't want to take part or if they have any questions later on. In both cases they should speak to their teacher who can let us know. Prior to completing the measures in class, children will be shown a short animation explaining what they are being asked to do and why. This will explain that they can choose not to answer the questions if they don't want to and that they can ask their teacher if they have any questions. Researchers will then answer any questions the children may have before they hand out the questionnaires.

Parents will be given information about the trial which will include contact details. The process for withdrawing data and consent will be explained in this information sheet.

Parents will give active consent for completing questionnaires about their child, for their child to be observed playing (in a way that leads to information about an individual child's play) and for their child to participate in a qualitative interview. Parent will be able to consent to any, all, or none of these, as they wish; there will be no pressure to consent.

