### 7.6 Baseline data

Baseline data includes:

- Parent-report questionnaires
- Teacher-report questionnaires
- Child-report questionnaires
- Observations of play

Other measures and information are sought via interviews for a qualitative evaluation of the intervention and process evaluation of the intervention implementation and research.

Each are outlined in the table below under relevant headings. Note that most measures are included because they would be used in a full RCT to examine the primary or secondary outcomes, or to examine whether the programme successfully changes play (the proposed mechanism through which the programme would affect mental health). We have explained the relevance of each measure to a full RCT. Because this is a feasibility trial, the research questions focus on the feasibility of using these measures within a full RCT.

Parent report measures		
ars R-4 (at baseline)		
The data will be used to describe the sample and to ensure sufficient diversity in the focal observation subsample (see below), where we want to ensure diversity in child sex, age, ethnicity and wellbeing.		
Child internalising problems, as measured via the SDQ internalising subscale would be compared from baseline to posttest.		
We will use the Ofsted questionnaire to give us insight into whether the play programme has affected children's enjoyment of school and parent's perceptions of the school in a broad sense.		
The CHU9D will be used in a full RCT for health economics evaluation by providing Quality Adjusted Life Years (QALYS).		
The resource use questionnaire will be used in a full RCT for health economics evaluation, comparing service use between those who attend the intervention school and those who attend control schools.		

(children YR to Y4 at baseline)		
SDQ with impact section	Child internalising problems, as measured via the SDQ internalising subscale would be compared from baseline to posttest (likely primary outcome measure for full RCT).	
Child self-report measures		
Activities During Playtime questionnaire	This measure allows children to tell us about what they play and will provide insight into how play has changed in terms of activities. It contributes to analysis of the extent to which the programme changes play (the proposed action through which is may affect mental health).	

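### Section 10 names a chi-square test for the missing-data criterion and also says no significance tests will be performed; if teacher forms go missing by class, an ordinary chi-square would be anti-conservative

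*Protocol*

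**What the plan says.** The progression criteria are the primary outcome of this feasibility trial (Section 3.4). One Green criterion reads: "No marked differences in the characteristics of the children with missing data on teacher report measures when compared to those with complete data". Its Amber counterpart accepts "Any differences in the characteristics of the children with missing data on teacher report measures" provided that statistical methods can deal with them. No size is attached to *marked*.

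Section 10 names one analysis that bears on this criterion: "Comparison using chi-square analysis of those with missing data vs. complete data on teacher report SDQ on demographic characteristics". It mentions no allowance for class or school. The closing paragraph of the same section begins: "As this is a feasibility study, significance tests will not be performed".

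On data collection, Section 7.2 has the headteacher consent "for teachers of children in Year R to Year 4 to complete a questionnaire for all children in their class". Parent questionnaires need active consent from the parent. In the Section 7.6 table, the entry for sample description stands under the parent-report measures: "The data will be used to describe the sample and to ensure sufficient diversity in the focal observation subsample". That table is damaged in the text available, and the name of the measure in this row is lost.

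**The concern.** There are three difficulties, of decreasing certainty.

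1. **Wording.** A chi-square comparison is ordinarily a significance test, and the section that specifies it says that none will be done. No descriptive measure or threshold is offered in its place, so two analysts could apply the criterion differently.
2. **Clustering.** If one teacher does not return forms, about 30 children go missing together. Children in one school also tend to share characteristics. An ordinary chi-square ignores both facts and would then flag chance differences between schools too often.
3. **Size versus significance.** Since *marked* is undefined, a p-value may come to stand in for it. The gap needed for significance grows as fewer children are missing.

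At stake is whether this criterion is scored Green or Amber, and whether the report describes selective loss correctly for planning the full trial.

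**Working it through.** **The plan's own figure.** Section 5 gives 8 schools. Section 6.1 gives about 30 children per year group or more. Section 7.2 covers Year R to Year 4, which is 5 year groups. 8 × 5 × 30 = 1200, which matches the approximate 1200 children in the data management plan (Section 11.1, item 1.3).

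**Assumptions not in the protocol.** Two-sided alpha 0.05; a yes/no characteristic with 20% prevalence; school ICC of that characteristic 0.02 to 0.15; 20% missing (240 of 1200, the most that the Green baseline rate of 80% allows).

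**Clustering.** Simulation with 4000 runs per setting: 8 schools × 5 classes × 30 children, beta-binomial characteristic by school, no true link between characteristic and missingness, ordinary Pearson chi-square. *All whole-class* means 8 of 40 classes missing. *Half whole-class* means 4 of 40 classes missing (120 children), plus each of the other 1080 children missing with probability 120/1080. Share of runs with p < 0.05:

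| School ICC | Unrelated to cluster | Half whole-class | All whole-class |
|---|---|---|---|
| 0.02 | 4.7% | 6.9% | 10.6% |
| 0.05 | 4.8% | 12.0% | 18.4% |
| 0.10 | 4.9% | 17.6% | 28.2% |
| 0.15 | 4.6% | 22.4% | 35.5% |

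Repeat runs with other seeds agree within about two percentage points, hence the rounded ranges of about 11–36%, 8–23% and 5%. If missingness instead varies by school (ICC of missingness 0.2), rejection is 10.5%, 17.9% and 29.1% at ICC 0.02, 0.05 and 0.10.

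A rough analytic check for whole-class loss uses the design effect 1 + (30 − 1) × ICC, which gives 1.58, 2.45, 3.90 and 5.35. The implied error, 2 × [1 − Φ(1.96/√Deff)], is 11.9%, 21.0%, 32.1% and about 40%. This is somewhat above the simulation, as expected, because missing and complete classes within the same school share the school effect.

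**Size of difference flagged.** Smallest significant observed gap = 1.96 × √[p(1−p)(1/n₁ + 1/n₂)], taking characteristics as known for all 1200 children and ignoring clustering:

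| Missing | Gap, p = 0.20 | Gap, p = 0.50 | Gap ÷ √[p(1−p)] |
|---|---|---|---|
| 240 (vs 960) | 5.7 points | 7.1 points | 0.14 |
| 60 (vs 1140) | 10.4 points | 13.0 points | 0.26 |

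The last column is the standardised difference at which p reaches 0.05. It nearly doubles between the two rows, although the meaning of *marked* should not change.

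**The case against.** The strongest case on the other side has five parts.

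- **The ban may cover intervention effects only.** The sentence opens a paragraph whose next sentence is about intervention effects, and Section 3.1 says that no hypotheses are evaluated. A reader might infer that Section 10 plainly forbids its own test; the text does not go that far. Still, the sentence is unqualified and its stated reason applies to the whole study, so the wording needs settling.
- **Nothing says that p < 0.05 decides the criterion.** This is correct. No alpha or decision rule is given, and the size-versus-significance point is therefore conditional.
- **Clustered missingness is not stated.** Section 7.2 also gives child-level routes to missing data, namely parental and child refusal. A reader might infer that the chi-square is simply invalid. That does not follow: with missingness unrelated to class or school, the error stays near 5%. Whole-class completion by one teacher makes some clustering likely, no more than that.
- **Demographics from responding parents only.** A reader might infer this from the Section 7.6 table. The protocol never says it, the table row is broken, and year group is known from the class being rated. What can be said is that the parent questionnaire appears to be the only demographic source visible.
- **The harm is limited.** With 60 of 1200 missing, even a 13-point gap moves the complete-case prevalence by only about 0.05 × 13 = 0.65 points from the full sample. A false alarm leads to Amber, which still permits progression.

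A statistical analysis plan could add a threshold or a cluster adjustment. The protocol has, however, already named the method and made the conflicting statement, so the correction belongs there.

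**Conclusion.** The point holds in a measured form. Section 10 specifies a chi-square comparison and says that significance tests will not be performed, and the two statements must be reconciled. As named, the test makes no allowance for class or school. It would be anti-conservative if missingness is clustered, which whole-class completion makes likely but which the protocol does not state. The size is about 11–36% false rejection if all missingness is whole-class, about 8–23% if about half is, and about 5% if it is unrelated to cluster. These figures rest on assumed prevalence, ICC, proportion missing and alpha. The dependence of the flagged gap on the number missing matters only if a p-value is used to define *marked*. The consequence is a possible mis-scoring of one criterion between Green and Amber; progression is not blocked. The change is worth making because it is cheap and concerns a stated method.

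**What to change.** In Section 10:

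1. Replace the chi-square with descriptive standardised differences (missing versus complete teacher SDQ) for each characteristic, overall and by arm. This also removes the conflict with the no-testing sentence.
2. State in advance the size that counts as *marked*, to be set by the sponsor, so that the Green and Amber wording can be applied.
3. Report how much of the missingness is whole-class or whole-school.
4. Name the source of the characteristics. Include year group, which the class gives for every child, and any other characteristic already available for all children. Report how many children lack parent-supplied characteristics.

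The cost is a wording amendment, which under Section 13.10 goes to the ethics committee before it is implemented, and a small amount of extra descriptive analysis. Design and sample size are unaffected. Any new class-list item would have to be covered by the school's consent and by ethics approval, since the headteacher consent described in Section 7.2 covers questionnaires and group-level playtime observation but does not mention class-list records.

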#### 11 DATA MANAGEMENT

### 11.1 Data collection tools and source document identification

Data management plan as approved by funder, copied below.

#### 0. Proposal name

Adventurous play as a route to decreasing children's risk for anxiety.

### 1. Description of the data

### 1.1 Type of study

Data will be collected from human subjects within a feasibility randomised control trial of a school-based play intervention.

